**A New Heat Therapy Device for Home-based Leg Heating in Patients With Lower-extremity Peripheral Artery Disease**

**NCT05335161**

**February 22, 2022**

## **1. Background and Rationale**

Peripheral artery disease (PAD) is a chronic condition characterized by impaired blood flow to the lower extremities. It is prevalent in older adults and is associated with mobility impairment, pain, and increased risk of cardiovascular events. Previous studies have suggested that heat therapy may improve vascular function and limb perfusion in patients with PAD. This study aims to develop and test the feasibility of a novel home-based leg heat therapy system specifically designed for patients with lower extremity PAD.

## **2. Objectives**

The primary goal of this study is to design a clinical-grade, easy-to-use leg HT system for elderly individuals suffering from PAD. Building on an existing cryotherapy water-circulating device designed for sports recovery, we will develop a new prototype system consisting of leg sleeves composed of an inner layer of polyurethane water-circulating pads and an outer layer of six inflatable bladders. The feasibility and safety of the prototype units will be evaluated in a single-arm pilot trial involving six patients with symptomatic PAD. The primary outcomes are completion rates, safety, and device usability. Secondary outcomes included changes in 6-minute walk distance, calf strength, performance on the five times sit-to-stand test, and quality of life as measured by the Walking Impairment Questionnaire (WIQ).

## **3. Participants**

Patients with symptomatic PAD will be recruited through flyers, online advertisements, and referrals from local peripheral vascular disease clinics. Men and women 60 years or older with a resting ABI of  $\leq 0.90$  in at least one leg were included in the study. Individuals with a resting ABI of  $>0.91$  at baseline will be eligible if their ABI decreases by  $\geq 20\%$  after a heel-rise test. The exclusion criteria include the presence of critical limb ischemia (ischemic rest pain or ischemia-related, nonhealing wounds, or tissue loss), prior leg amputation, exercise tolerance limited by factors other than leg pain (eg, angina, arthritis, severe lung disease, etc), recent lower extremity revascularization or orthopedic surgery, use of a walking aid other than a cane, active cancer, chronic kidney disease (estimated glomerular filtration rate of  $<30$ ), inability to fit into water-circulating trousers, a Mini-Mental Status Examination score of  $<23$ , and impaired thermal sensation in the leg.

## **4. Experimental protocol**

Participants will attend two baseline laboratory visits. Before each session, they will be instructed to fast overnight, avoid exercise for 24 hours, and refrain from smoking for 4 hours. During the first visit, participants will receive informed consent, complete a medical history form, have their leg symptoms assessed using the San Diego Claudication Questionnaire, complete the Mini-Mental Status Examination, and undergo a thermal sensation test with heating pads on their thighs and calves. The ABI will be assessed following American Heart Association guidelines. After a 10-minute rest, a handheld Doppler ultrasound probe will be used to measure systolic pressures in the posterior tibial, dorsalis pedis, and brachial arteries. The ABI for each leg will be calculated

by dividing the average dorsalis pedis and posterior tibial pressures by the average brachial pressures. Participants will then be familiarized with the 6-minute walk test, isokinetic calf strength testing, and the five-times sit-to-stand test.

The second visit, conducted at least 48 hours later, will include (1) blood pressure measurement, (2) a 6-minute walk test, (3) torque assessments of the plantar flexors using an isokinetic dynamometer, (4) the five-times sit-to-stand test, and (5) quality of life assessment via the WIQ. After completing baseline tests, participants will undergo a supervised 90-minute treatment session with the prototype HT device to monitor acute changes in skin temperature and blood pressure. Thermocouples (MLT422; AD Instruments, Colorado Springs, CO) will be taped to the calf and thigh to measure leg skin temperature, and systolic and diastolic blood pressures will be recorded every 5 minutes.

Participants will be given the prototype device for daily use while lying down or seated with legs extended. They will log therapy sessions and measure blood pressure before and after each session using a portable monitor (Omron 3 Series Upper arm, Omron Healthcare Co. Ltd., Kyoto, Japan). Weekly check-ins with the study coordinator will track therapy dates, times, blood pressure readings, and any adverse effects. Outcomes will be reassessed at the end of the 12-week intervention, with participants stopping treatment 48 hours before the final evaluations to isolate chronic effects.

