## 5. Outcome measures

### Feasibility end points (primary outcomes)

The completion rate will be determined by monitoring the number of participants who finish the study protocol within the specified timeframe compared to the total number enrolled in the study.

**Safety:** Safety will be evaluated by monitoring adverse events. The research coordinator will call patients weekly to record any adverse events during the intervention.

**Device usability:** Participants will be asked to rate the device usability at the end of the experiment using the System Usability Scale. The psychometric properties of the System Usability Scale have been established, including its reliability and sensitivity.

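### Usability is rated only at the end of the experiment, so a participant who leaves before week 12 has no scheduled rating and one who stops heating but stays is rated weeks after last use

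*Combined protocol and SAP*

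**What the plan says.** Section 2 sets the endpoints: "The primary outcomes are completion rates, safety, and device usability". For usability, section 5 states: "Participants will be asked to rate the device usability at the end of the experiment using the System Usability Scale". It gives no other rating time, and section 6 has no rule for a missing rating. Section 6 names improving the device design as part of the trial's main goal.

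Home treatment is described in section 4: "Participants will be given the prototype device for daily use while lying down or seated with legs extended". Follow-up during that period is by weekly contact: "Weekly check-ins with the study coordinator will track therapy dates, times, blood pressure readings, and any adverse effects". Section 5 also has the coordinator telephone each week to record adverse events. The only instruction to stop heating is tied to the final tests: "Outcomes will be reassessed at the end of the 12-week intervention, with participants stopping treatment 48 hours before the final evaluations".

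Section 5 defines completion as the number who get through the protocol on time, relative to the number enrolled. Section 3 excludes people with critical limb ischemia or "impaired thermal sensation in the leg". Thermal sensation is tested at the first visit, where participants "undergo a thermal sensation test with heating pads on their thighs and calves". No later section applies the exclusions again.

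**The concern.** A prototype tested in six people is most usefully criticised by those who could not go on using it. The plan collects its usability score at the moment when such people are most likely to be gone, or no longer to have the device fresh in mind. If an early leaver found the device harder to use than the others did, losing that rating makes the mean look better than it should, and the design team loses the comments it most needs.

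Two related gaps concern the same participants. The text does not say whether a person who gives up heating but attends the 12-week tests has completed. It also names no harm that obliges an individual to stop heating at home.

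**Working it through.** **Inputs.** Six participants, single arm (section 2); 12 weeks of daily use, ending 48 hours before the final tests (section 4); one usability rating at the end (section 5). The plan states no figure for usability, so there is none to reproduce. The score gap d, the number of unrated participants m and the stop risk p are not in the documents and are assumed below.

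**1. Who is rated, and when.**
- Finishes as planned: rated at the end, about 48 hours after the last session if the rating accompanies the final tests.
- Stops heating, stays to week 12: section 5 does not restrict the rating to completers, so this person would probably be asked. The delay since last use is 12 minus the stop week: 12 − 2 = 10, 12 − 3 = 9 or 12 − 6 = 6 weeks.
- Leaves before week 12: no rating is scheduled.

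**2. Effect of a missing rating on the mean.** Let those who are rated average μ, and let m unrated participants average μ − d.

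Mean of all six = [(6 − m)μ + m(μ − d)] / 6 = μ − m·d/6.

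The reported mean is μ, so it is too high by m·d/6:

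| m | d = 10 | d = 20 | d = 40 |
|---|---|---|---|
| 1 | 1.7 | 3.3 | 6.7 |
| 2 | 3.3 | 6.7 | 13.3 |

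Example with assumed scores: five participants rate 80 and the sixth would have rated 40. The mean of six is (5 × 80 + 40)/6 = 73.3; with the sixth unrated it is 80, a difference of 6.7.

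**3. How easily one safety stop could arise.** With an assumed risk p per participant, the chance of at least one among six is 1 − (1 − p)^6: 26%, 47%, 74% and 88% for p = 5%, 10%, 20% and 30%. Not every such person would leave, so this is an upper guide to missing ratings from safety stops.

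**4. Completion.** One participant who stops heating for good but attends the final tests can be counted either way: 6/6 = 100% (exact 95% CI 54 to 100) or 5/6 = 83% (36 to 99.6). The step is 1/6 = 16.7 points. It shows what one classification is worth, not how likely the case is.

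**5. Time from a harm to the next call.** Twelve weeks less 48 hours is 84 − 2 = 82 daily sessions. With calls after every seventh session and a last interval of five, the further sessions between an event and the next call sum to 11 × (0+1+…+6) + (0+1+2+3+4) = 231 + 10 = 241. The mean is 241/82 = 2.9 and the maximum 6. This assumes that nobody reports between calls and that use continues.

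**The case against.** The strongest reply is that section 5 asks participants, without restriction, to rate the device at the end, and that the end could mean each person's own last day in the trial. That reading would cover early leavers, but it is not stated and no early-termination visit or contact is described to carry it out. What stands is that a participant who stops heating but stays would probably be rated. A reader might therefore infer too much by concluding that the score comes only from those able to continue; the text does not support that. The formula in step 2 applies only to people who are never rated.

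A reader might also infer that someone who pauses, restarts and finishes on time, or someone who refuses the device after the supervised session, has no completion status. The ordinary meaning of the definition settles both: the first has finished and the second has not. Only the participant who stops heating and attends the final tests is open.

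Nor can one conclude that participants get no instruction on when to stop. The consent pages were removed from the file and may contain it, staff may act on what they hear, and nothing says participants cannot telephone between calls.

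Finally, this is an exploratory pilot of six with no usability or completion threshold, so each case can be described individually. That limits the consequence, but a rating that was never collected cannot be described.

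**Conclusion.** The concern holds for the timing of the usability rating. As written, an early leaver has no scheduled rating, and a participant who stops but stays is rated late. The mean is too high by m × d / 6 if those missing would have scored lower: 1.7 to 6.7 points for one unrated participant and 3.3 to 13.3 for two, over assumed gaps of 10 to 40 points. The direction rests on the assumption that early leavers rate the device lower, which is plausible but not shown by the documents. No stated decision depends on the score; what is affected is the reported figure and its use in redesign and planning.

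The completion status of a participant who stops heating but attends the final tests, and the absence of a stop rule from the protocol text, are secondary. Both are missing detail that is easily supplied, and the second may already be covered in the consent pages.

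**What to change.** **Section 5, usability (main change).** Add: 'A participant who permanently stops home use, for any reason, completes the System Usability Scale at the next weekly call. The score is reported with and without these participants.' The cost is one telephone questionnaire per early stop, on a call that is already planned, and possibly a less favourable score. Someone who declines further contact would still be unrated and should be listed as such.

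**Section 5, completion.** Add that a participant who permanently stops heating is a non-completer even if the 12-week tests are attended. Compared with the other reading, each such case lowers the rate by 1/6, or 16.7 points, when six are enrolled.

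**Section 4, stopping.** Add that home use stops for a burn, blister, skin break, faint or newly developed section 3 exclusion, and restarts only after investigator assessment. If the consent pages already say this, a cross-reference is enough. The cost is an assessment before each restart, which may need an unscheduled visit, and perhaps more stops than staff judgement alone would produce; the documents give no rate from which to estimate how many. The rule relies on participants noticing and reporting lost sensation, and it sets no limit for home blood pressure. Whether to add a repeat sensation test or such a limit is for the investigators.

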## 5. Outcome measures

### Feasibility end points (primary outcomes)

The completion rate will be determined by monitoring the number of participants who finish the study protocol within the specified timeframe compared to the total number enrolled in the study.

**Safety:** Safety will be evaluated by monitoring adverse events. The research coordinator will call patients weekly to record any adverse events during the intervention.

**Device usability:** Participants will be asked to rate the device usability at the end of the experiment using the System Usability Scale. The psychometric properties of the System Usability Scale have been established, including its reliability and sensitivity.

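### Safety is a primary outcome, but no leg or skin inspection or skin-event prompt is specified, so skin events rest on participant report and may be under-counted

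*Combined protocol and SAP*

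**What the plan says.** Section 2 states: "The primary outcomes are completion rates, safety, and device usability". The device is a prototype with "leg sleeves composed of an inner layer of polyurethane water-circulating pads and an outer layer of six inflatable bladders", to be "evaluated in a single-arm pilot trial involving six patients with symptomatic PAD".

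Section 5 (Feasibility end points) defines the safety outcome in two sentences. The first is "Safety will be evaluated by monitoring adverse events"; the second gives the method: "The research coordinator will call patients weekly to record any adverse events during the intervention". Section 4 describes what is evidently the same contact: "Weekly check-ins with the study coordinator will track therapy dates, times, blood pressure readings, and any adverse effects". On home recording it adds: "They will log therapy sessions and measure blood pressure before and after each session using a portable monitor".

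Section 3 excludes people with critical limb ischemia, which the plan defines to include wounds that do not heal and tissue loss, and people with "impaired thermal sensation in the leg". Section 4 tests thermal sensation once, at the first baseline visit. For the end of the study it says only that outcomes are reassessed after a 48-hour break from treatment.

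**The concern.** The plan screens out people whose legs are most vulnerable to heat or skin breakdown. It then sends a heated, inflating sleeve home for 12 weeks of daily use by people aged 60 or older with arterial disease of the legs. It is a fair inference that skin injury is a foreseeable harm, yet no step in the plan records skin condition by observation. Such an event enters the safety outcome only if the participant notices it and mentions it on the telephone.

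With six participants, one missed lesion changes the result. Section 6 says the data are meant to refine the device and inform larger studies, and an unrecorded skin finding is information lost for both. Without a baseline skin record, a minor mark seen at 12 weeks also cannot be classed as new or old.

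**Working it through.** **Step 1. What each contact is said to record.**

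| Contact | Stated content | Skin condition |
|---|---|---|
| Visit 1 (Section 4) | Ankle pressures by Doppler; heating-pad sensation test on thighs and calves | Not stated |
| Visit 2, supervised session (Sections 4, 6) | Skin temperature by thermocouple; blood pressure every 5 minutes | Temperature only |
| Home log (Section 4) | Sessions; blood pressure before and after | Not stated |
| Weekly call (Sections 4, 5) | Session dates and times, blood pressure, adverse effects or events | Only if reported; no prompt listed |
| 12-week evaluation (Section 4) | Outcomes reassessed, not itemised | Not stated |

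No row specifies an inspection, and no section lists burn, blister, sore or other skin change as something to ask about.

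**Step 2. Is there a figure to reproduce?** No. The plan gives no expected event rate and no capture rate, and Section 6 states that no power analysis was done. The rest illustrates how much capture could matter under assumed inputs.

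**Step 3. Chance that no participant is recorded with an event.** Inputs: n = 6 (Section 2); p, the true risk per participant (assumed); s, the share of affected participants captured by report (assumed). With independent participants, P(0 recorded) = (1 − p·s)^6.

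| p | s = 1 | s = 0.75 | s = 0.5 | s = 0.25 |
|---|---|---|---|---|
| 10% | 0.53 | 0.63 | 0.74 | 0.86 |
| 20% | 0.26 | 0.38 | 0.53 | 0.74 |
| 30% | 0.12 | 0.22 | 0.38 | 0.63 |

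For example, at p = 0.2 and s = 0.5: (1 − 0.1)^6 = 0.53.

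**Step 4. What 0/6 would rule out.** The one-sided 95% upper bound with full capture is 1 − 0.05^(1/6) = 0.393. Dividing by s gives 0.393/0.75 = 52% and 0.393/0.5 = 79%. At s = 0.25 the quotient exceeds 1, so the bound is uninformative. Even with perfect capture, 0/6 is compatible with a true risk of up to 39%.

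**Step 5. Sensitivity to repeated calls.** Suppose 2 of 6 are truly affected. The chance that neither is recorded is (1 − s)^2, which is 0.25 at s = 0.5 and 0.01 at s = 0.9. If 50% is instead the capture per call, and a lesion spans two calls treated as independent, then s = 1 − 0.5^2 = 0.75 and the chance falls to 0.25^2 = 0.06. The answer therefore runs from 1% to 25% on assumptions that the documents cannot settle.

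**The case against.** The calls are weekly and active, not left to spontaneous reporting, and the endpoint covers any adverse event. People with impaired heat sensation or a Mini-Mental score below 23 are excluded, so unnoticed injury and poor recall are less likely among those enrolled. This is an exploratory pilot of six. All of that stands; it lowers the likely size of the problem. It does not put an observation of the skin into the plan.

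Four stronger readings are tempting, and the documents do not support them:

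- **That the exclusions name heat injury as a risk.** They do not. Neither heat injury nor burns are mentioned. The link from the thermal sensation exclusion is an inference, and the limb ischemia exclusion may simply define the study population.
- **That nobody looks at the legs.** Staff take ankle pressures, place heating pads and attach thermocouples at the baseline visits, and excluding wounds or tissue loss implies some assessment at entry. The plan is silent on a recorded inspection; silence does not show that none takes place. Nor does it show that safety is left out at 12 weeks, since the outcomes to be reassessed there are not itemised.
- **That the term adverse effects in Section 4 narrows the endpoint to what participants blame on the device.** Section 5 defines the endpoint and uses the wider term. This is loose wording that needs aligning.
- **That no later lesion could be classed as new.** Ischemic wounds and tissue loss are excluded at entry, so the most serious lesions would be new. The difficulty is confined to minor marks.

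**Conclusion.** The point holds as a gap in ascertainment. The only stated route to a primary outcome is participant report by weekly call, with no specified skin inspection and no skin-event prompt, so skin events may be under-counted. The direction follows from the fact that missed events can only lower the count of true events. The size is unknown: every figure in the working beyond the six participants and the full-capture bound of 39% depends on an assumed risk or capture rate, and on independence between participants.

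A reader might go further and conclude that the safety result is biased low by a material amount. The documents do not show that. This is a worthwhile, inexpensive improvement to measurement and does not invalidate the trial.

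**What to change.** 1. At visit 2, before and after the supervised session, and at the 12-week evaluation, have the attending staff inspect both bared legs and feet and record the findings on a short form.
2. Add tick-boxes to the existing session log for redness, blister or sore, pain, numbness and dizziness, and review them in each weekly call. This part is essential: an inspection 48 hours or more after the last session will miss transient redness and healed lesions. It remains self-report, but it is prompted and dated.
3. Use one definition in Sections 4 and 5: *adverse events, whether or not thought related*.
4. Count in the safety outcome any finding that is new relative to the visit 2 pre-session record.

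The change concerns measurement only and leaves treatment untouched. The cost is a few minutes at two existing visits and an addition to an existing log, with no extra visit or equipment. The downside is a slightly higher count that may include background skin changes, which cannot be separated from device effects without a control arm.

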### Secondary outcomes

**6-Minute walk test:** Participants will receive standardized instructions and be asked to walk the greatest distance possible by walking back and forth along a 100-ft corridor for 6 minutes.

**Blood pressure:** Blood pressure measurement will be conducted using an automated device (Tango+, Suntech Medical, Morrisville, NC), following the recommendations of the American Heart Association.

**Calf strength:** Torque assessments of the plantar flexors of the most symptomatic leg or the leg with the lowest ABI will be conducted using an isokinetic dynamometer (Biodex System 4 Pro, Biodex Medical Systems, Shirley, NY). The participants will be positioned supine on the

dynamometer chair with their knees flexed at 90°. Before maximal testing, they will complete a standardized warm-up consisting of three submaximal contractions, each held for 5 seconds at approximately 50% of perceived maximal effort. Following the warm-up, participants will perform three maximal voluntary isometric contractions, each lasting 5 seconds, with a 60-second rest period between attempts to minimize fatigue. Standardized verbal encouragement will be provided during each maximal voluntary isometric contraction to ensure maximal effort. The trial that produces the highest peak torque value (in N·m) will be selected for analysis.

**The Five Times Sit-to-Stand Test:** Participants are asked to sit in a chair with arms folded across their chest and stand five times in a row as quickly as they can. The time it takes to complete five chair rises is recorded.

**WIQ:** Patient-reported perceptions of walking ability will be assessed using the WIQ. This disease-specific questionnaire assesses the ability of patients with PAD to walk defined distances and speeds and to climb stairs, with scores ranging from 0 to 100.30. Higher scores reflect better community-based walking ability.

